# 6.4 Duration of episodes with SpO2 continuously <80% for manual and automated control epochs

This will be summarised as the median and range within each treatment.

# 6.5 Proportion of time (over total usable time) with SpO2 >96% when receiving supplemental oxygen (hyperoxaemia)

This will be measured as percent time when in oxygen. This will be analysed in the same way as the primary outcome. The same subgroup analyses as specified for the primary outcome will be done.

# 6.6 Proportion of time (over total usable time) with SpO2 >98% when receiving supplemental oxygen (severe hyperoxaemia)

This will be measured as percent time when in oxygen. This will be analysed in the same way as the primary outcome.

#### 6.7 Frequency of 30s episodes with SpO2 continuously >96% (hyperoxaemic episodes)

This will be measured as number of episodes per hour and analysed in the same way as Secondary objective 6.3.

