## 2.1. Primary Objective and Outcome

The primary objective of this trial is to evaluate the impact of OxyMate on safe oxygen saturation targeting compared to manual control of oxygen for preterm infants in Nigeria.

The primary outcome is: Proportion of time (over total recorded time) in the target  $SpO_2$  range (91-95%, or 91-100% when in room air). This will be measured as percent time, where the denominator is usable time, excluding all periods during which the  $SpO_2$  values are missing.

Secondary outcome for the primary objective: Proportion of time (over total usable time) in SpO2 target range (91-95%) when receiving supplemental oxygen. This will be measured as percent time when in oxygen.

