2.2. Secondary Objectives and	
OBJECTIVE	OUTCOME & OUTCOME MEASURE
To evaluate whether OxyMate	Proportion of time (over total usable time) with SpO 2 <90%
prevents time in, and episodes of,	(hypoxaemia). This will be measured as percent time.
hypoxaemia compared to manual	Proportion of time (over total usable time) with SpO 2 <80% (severe
control of oxygen.	hypoxaemia). This will be measured as percent time.
	Frequency of 30s episodes with SpO 2 continuously <80% (severe
	hypoxaemic episodes). Measured as mean number of episodes per
	hour.
	Duration of episodes with $SpO_2$ continuously <80% for manual and
	automated control epochs. Measured in seconds.
To evaluate whether OxyMate	Proportion of time (over total usable time) with $SpO_2 > 96\%$ when
prevents time in, and episodes of,	receiving supplemental oxygen (hyperoxaemia). Measured as percent
hyperoxaemia compared to	time when in oxygen.
manual control of oxygen.	Proportion of time (over total usable time) with $SpO_2 > 98\%$ when
	receiving supplemental oxygen (severe hyperoxaemia). Measured as
	percent time when in oxygen.
	Frequency of 30s episodes with $SpO_2$ continuously >96%
	(hyperoxaemic episodes). Measured as mean number of episodes per hour.
	Dduration of episodes with SpO 2 continuously >96% for manual and automated control epochs. Measured in seconds.
To evaluate whether OxyMate	Frequency of manual $FiO_2$ adjustments in both manual and automated
reduces nursing workload	arms. This is measured as mean number of FiO 2 adjustments/hour.
compared to manual control of	
oxygen.	
To evaluate whether OxyMate is	Number and duration of periods of no $FiO_2$ increment for $\geq 30s$ with
safe compared to manual control	$SpO_2 < 80\%$ (i.e. failure to respond to severe hypoxaemia). Measured
of oxygen.	as mean number of episodes per hour, and mean duration per
	episode.
	Number and duration of periods with $SpO_2 < 80\%$ for $\ge 30s$ with any
	bradycardia (heart rate <100 bpm). Measured as mean number of
	episodes per hour, and mean duration per episode.
	Number of OxyMate malfunction events
To evaluate whether OxyMate is	Score on User Survey questions using Likert scale.
acceptable and feasible to	
healthcare workers.	
To evaluate the cost of OxyMate.	Total costs of prototype system (Diamedica +/- oxygen automation)
To evaluate participants duration	Duration of time on CPAP with supplemental oxygen. Measured in

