# 5. ANALYSIS OF THE PRIMARY OUTCOME(S)

## 5.1. Main Analysis

Primary outcome: Percent of time (over total recorded time) in the target  $SpO_2$  range (91-95%, or 91-100% when in room air).

Cross-over studies introduce risks of carry-over and period effects, and we have attempted to account for these in the study design. We consider carry-over effects to be small given that change from one mode of control to the other is instantaneous. We have allowed for a 1-hour change over period where data are not

Statistical Analysis Plan

included in the analysis. Period effects are possible with changes in practice over the study period for each infant but large changes in care over the 48 hour study period are unlikely. The clinical condition of infants will be dynamic and may change over the study period, but the primary outcome of time in target SpO2 range will be comparable irrespective of the clinical course of an infant as long as they remain on oxygen.

We will compare mean percentage time in target SpO2 range (y in code below) between the two 24 h arms of manual and automated control using weighted repeated measures mixed model linear regression adjusting for randomised group, treatment (manual vs automated), period, repeated measure in the same participant and facility (site). All infants will be included in this analysis, even those who do not provide complete studies. The weights will be calculated as the reciprocal of the total time in manual and automated control divided by 24 hours for each period separately. Infants who provide complete studies will have a weight of 1.

The following Stata code will be used:

xtmixed y treatment randomised\_group period site [pw = weight] || participant: period

We will plot the primary outcome across the treatments for individual participants using spaghetti (line) plots. The x-axis will represent manual and automated, while the y-axis will be the percent of time in target range. The colours of the lines will represent the randomisation (which treatment was received first) and complete studies will be indicated with solid lines and incomplete studies with dashed lines.

Secondary outcome for the primary objective: "Proportion of time (over total usable time) in SpO2 target range (91-95%) when receiving supplemental oxygen", measured as percent time when in oxygen, will be analysed in the same way as described for the primary outcome.

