# 6.8 Duration of episodes with SpO2 continuously >96% for manual and automated control epochs

This will be summarised as the median and range within each treatment.

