#### **Figure 3: Histogram of proportion of time in different SpO2 ranges** Bars are presented by treatment

#### Table 9: Secondary outcomes analysed with Poisson regression

Variable			Automated Median (95% CI)	Manual Median (95% Cl)	Incidence rate ratio (Manual/ Automated) (95% CI)	p- value
----------	--	--	---------------------------------	------------------------------	------------------------------------------------------------	-------------

Frequency of 30s episodes with SpO2 continuously <80% (severe hypoxaemic episodes) Frequency of 30s episodes with SpO2 continuously >96% (hyperoxaemic episodes) Frequency of manual FiO2 adjustments Number of periods of no FiO2 increment for ≥30s with SpO2 <80% (i.e. failure to respond to severe hypoxaemia). Number of periods of with SpO2 <80% for ≥30s with any bradycardia (heart rate <100

**Listing 1: Oxymate malfunction events** Listing of timing and nature of all OxyMate malfunction events.

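### Hyperoxaemic episodes (SAP 6.7 and 6.8) lack the oxygen condition used in 6.5 and 6.6, so room-air time that is in target for the primary outcome also counts as an adverse episode

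*SAP*

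**What the plan says.** The primary outcome, in SAP 2.1 and again in 5.1, is percent time in a target range of "91-95%, or 91-100% when in room air". High saturation without added oxygen is therefore a success.

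The hyperoxaemia objective in the 2.2 table has four outcomes. The two time outcomes carry an oxygen condition, repeated in 6.5 (">96% when receiving supplemental oxygen (hyperoxaemia") and 6.6 (">98% when receiving supplemental oxygen"). The device-deficiency definition in 3.4 also ties severe hyperoxaemia to receiving oxygen.

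The two episode outcomes carry no such condition:

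- Frequency: 6.7 has "continuously >96% (hyperoxaemic episodes", the 2.2 table has "hyperoxaemic episodes). Measured as mean number of episodes per hour", and the Table 9 shell lists the row without an oxygen limit.
- Duration: 6.8 has "continuously >96% for manual and automated control epochs", and its row in 2.2 is likewise unrestricted.

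Section 6.7 is analysed as in 6.3, where each infant's episode count is divided by the length of that infant's period in hours. That is the whole period, not time in oxygen.

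**The concern.** SpO2 of 97-100% in room air is scored in two opposite ways: as time in target for the primary outcome and as an adverse episode in 6.7 and 6.8. Room-air data are expected, since the primary outcome has its own room-air range. Under 2.6 and 3.7 an infant in room air becomes incomplete only once SpO2 has stayed above 95% for 4 hours, so shorter or interrupted spells remain in the data.

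At stake is the half of the objective that asks whether OxyMate prevents episodes of hyperoxaemia, which only 6.7 and 6.8 address. Section 6.7 yields an incidence rate ratio and p-value in Table 9. If room-air runs enter, that ratio mixes control of oxygen with time spent off oxygen. The trial is open label (2.5), so deciding after the data are seen whether room air counts would be a choice open to knowledge of the results.

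**Working it through.** **Plan's own figures.** The SAP gives no episode rate, room-air share or expected rate ratio, so there is no figure to reproduce for these outcomes. The 13 infants in 2.6 concern the primary outcome only. They reproduce with a two-sided paired t-test (difference 10, SD 10, alpha 0.05: power 0.883 at n = 12, 0.911 at n = 13) and are not affected.

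**Definitions side by side.** Take a run of at least 30 s at SpO2 97-100%, with usable readings:

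| Outcome | On supplemental oxygen | In room air |
|---|---|---|
| Primary (2.1, 5.1) | out of target | in target |
| 6.5, time >96% | counted | not counted |
| 6.6, time >98% (if reached) | counted | not counted |
| 6.7, episodes >96% | one episode | one episode |
| 6.8, episode duration | length included | length included |

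The room-air column is the contradiction.

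**Effect on the 6.7 rate ratio (illustration; every input is assumed).** Take 24 h periods with 6 h of room air under automated and 2 h under manual control, leaving 18 h and 22 h in oxygen. In-oxygen rates are 3/h automated and 6/h manual, so the in-oxygen ratio (manual/automated, the direction in Table 9) is 6/3 = 2.00. Let r be the number of room-air runs above 96% per room-air hour, the same in both modes.

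- Automated rate as written: (18 × 3 + 6r)/24 = (54 + 6r)/24
- Manual rate as written: (22 × 6 + 2r)/24 = (132 + 2r)/24
- Ratio: (132 + 2r)/(54 + 6r)

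| r per hour | Calculation | Ratio as written |
|---|---|---|
| 8 | 148/102 (6.17/h over 4.25/h) | 1.45 |
| 4 | 140/78 | 1.79 |
| 2.4 | 136.8/68.4 | 2.00 |
| 1 | 134/60 | 2.23 |
| 0.25 | 132.5/55.5 | 2.39 |

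Break-even solves 132 + 2r = 2(54 + 6r), giving r = 24/10 = 2.4. Above it the written definition understates the in-oxygen ratio; below it the definition overstates it, because room air adds hours to the denominator and few episodes to the numerator.

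**Equal room-air shares.** Now assume 1/h automated and 2/h manual in oxygen, and the same room-air share s in both modes. The ratio is [2(1 − s) + sr]/[(1 − s) + sr]. For r of 2 to 4 per hour:

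| s | Ratio as written (in-oxygen value 2.00) |
|---|---|
| 5% | 1.83-1.90 |
| 10% | 1.69-1.82 |
| 20% | 1.50-1.67 |
| 30% | 1.37-1.54 |

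With equal shares the ratio moves towards 1 for any r above zero. Movement in the other direction needs unequal shares.

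**Duration (6.8).** The summary is a median and range. One unbroken room-air run approaching 4 h, if kept, would be about 17% of a period (4/24 = 16.7%; 4/23 = 17.4%) and would set the top of the range unless a longer episode occurred.

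**The case against.** The strongest reply is that the condition is implied. Section 6.5 labels hyperoxaemia as an in-oxygen state, the objective groups time and episodes together, and 3.4 uses the same limit. This makes an omission more likely than a decision to count room air. It does not settle what will be programmed: within one objective, two outcomes state the condition and two do not, and the whole-period denominator fits the unrestricted reading.

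Room-air time may also be small. Entry requires supplemental oxygen and a projected need for CPAP and oxygen beyond 48 hours (2.3). Section 2.6 can be read as cutting the data at the start of a 4-hour run above 95%, which would remove the longest spells. Both points limit the size; neither removes shorter or interrupted room-air runs.

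A reader might infer that the definition is biased against OxyMate, on the view that automation weans infants to room air sooner and so collects more false episodes. The document does not support that. It does not say that OxyMate produces more room-air time, and even if it did, the direction depends on how often room-air runs occur: a continuous run counts once however long it lasts, so few or long runs shift the ratio in OxyMate's favour.

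Finally, these are secondary outcomes, 6.8 is only descriptive, and 6.5 and 6.6 still address time in hyperoxaemia. That is correct and bears on the severity.

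**Conclusion.** The inconsistency stands on the wording alone. Under the text of 6.7 and 6.8, the same room-air seconds are in target for the primary outcome and an adverse episode in a secondary one, and the 6.7 rate is taken over all time rather than time in oxygen.

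Neither the size nor the direction can be established from the SAP. In the main illustration an in-oxygen ratio of 2.00 is reported as anything from 1.45 to 2.39, depending on the assumed room-air run rate; the room-air hours and in-oxygen rates are also assumptions. The supportable statement is that the ratio depends partly on room-air time and how it breaks up, not that it favours either mode.

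This is a definition error in secondary outcomes, worth correcting before analysis. It does not touch the primary analysis, the in-oxygen companion outcome, 6.5, 6.6 or the sample size.

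**What to change.** 1. Add the supplemental-oxygen condition already used in 6.5 and 6.6 to 6.7, to 6.8, to both matching rows of the 2.2 table and to the 6.7 row of Table 9.
2. In 6.7, replace the whole-period denominator taken from 6.3 with usable hours in oxygen in that period, and use those hours as the exposure for the rate.
3. For a run that crosses between oxygen and room air, count and time only the in-oxygen portion, provided that it lasts at least 30 s. Do not require oxygen throughout the run: that would discard true in-oxygen episodes that ended with weaning to room air, and could do so unequally between modes. State also whether two in-oxygen stretches within one unbroken run count once or twice.

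This makes 6.7 and 6.8 conditional on time in oxygen, as 6.5 and 6.6 already are. The cost is SAP wording and a filter in the episode-detection code, using FiO2 data already needed for 6.5 and 6.6. No new data and no change in sample size are needed.

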# 6.8 Duration of episodes with SpO2 continuously >96% for manual and automated control epochs

This will be summarised as the median and range within each treatment.

#### 6.9 Frequency of manual FiO2 adjustments

This is measured as number of FiO2 adjustments/hour. This will be analysed in the same way as Secondary objective 6.3.

# 6.10 Number and duration of periods of no FiO2 increment for ≥30s with SpO2 <80% (i.e. failure to respond to severe hypoxaemia)

This is measured as number of episodes per hour and mean duration per episode. The number of episodes will be analysed in the same way as Secondary objective 6.3. For each infant the mean duration of all periods of failure to respond to severe hypoxaemia will be calculated. These means will be described and compared between the treatment arms using the same method as for the primary outcome.

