### Inclusion criteria:

• ≥12 hours old

- Receiving CPAP support and supplemental oxygen (FiO2 >0.21) for respiratory insufficiency
- Projected requirement for CPAP and oxygen therapy for >48 hours

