### Exclusion criteria:

- Deemed likely to fail CPAP in the next 48 hours, and would otherwise qualify for surfactant therapy and/or mechanical ventilation at initial assessment were it available: SpO2 <85% with FiO2 >0.50 on CPAP 8 cmH2O, clinical features of hypercapnic respiratory failure (hypoventilation, reduced level of alertness)
- Deemed clinically unstable or recommended for palliation by treating team
- Cause of hypoxaemia likely to be non-respiratory e.g. cyanotic heart disease
- Informed consent from parent/guardians not obtained

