## 3.4. Definitions related to Adverse Events (AEs)

	Definition	Effect	Mechanism linking device to effect
Adverse Device Effect (ADE)	Any untoward and unintended response to a medical device. This definition includes any event resulting from insufficiencies or inadequacies in the instructions for use or the deployment of the device.	
 
Death and serious adverse event (SAE)
 
Prolonged hypoxaemia
 
Prolonged hyperoxaemia
 
	
 
In OxyMate automated mode:
 
Failure to respond to SpO2 deviation, resulting in prolonged hypoxaemia or hyperoxaemia
 
Failure of alarms to alert health workers to rising oxygen requirement
 

Device deficiencies	Inadequacy of a medical device with respect to its identity, quality, durability, reliability, safety or performance. Device deficiencies include	
 
Prolonged (>30 s) episode of severe hypoxaemia (SpO2 <80%) without an increase in FiO2
 
Prolonged (>30 s)
 
	
 
Errors in:
 
Algorithm – failure to respond correctly to SpO2 data
 
Servomotor controller – failure to correctly adjust oxygen/air flow
 

	Definition	Effect	Mechanism linking device to effect			
	malfunctions, use errors and inadequate labelling.	episode of severe hyperoxaemia (SpO 2 >98% when receiving oxygen) without a decrease in FiO 2	
 
Alarms – failure to detect/alert to errors
 
			
Adverse Event (AE)	Any untoward medical occurrence in a participant administered a medicinal product and that does not necessarily have a causal relationship with this treatment.	
 
Death
 
Other clinical deterioration, new illness, or new injury
 
				
Serious Adverse Event (SAE)	
 
a life-threatening illness
 
a permanent impairment
 
prolonged hospitalisation
 
medical or surgical interv
 
	nt of a body structure or a body function, or				
Serious Adverse Device Event (SADE)	-	to a body structure or a body function An adverse device effect that has resulted in any of the consequences of a SAE.				
Unanticipated Serious Adverse Device Effect (USADE)	-	A serious adverse device effect which by its nature, incidence, severity or outcome has not been identified in the current version of the risk analysis report.				

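### SAP 6.10 scores time held at maximum FiO2 as failure to respond, because the definition does not require that FiO2 could still be raised

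*SAP*

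**What the plan says.** The objectives table in SAP 2.2 places this outcome under the objective on the safety of OxyMate compared with manual control. Section 6.10 defines the event by two conditions that hold together for at least 30 s: SpO2 below 80% and no FiO2 increment. It glosses the event as "i.e. failure to respond to severe hypoxaemia".

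Two measures are then compared between modes:

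- Count: "The number of episodes will be analysed in the same way as Secondary objective 6.3", which means a Poisson mixed model on episodes per hour.
- Duration: for each infant the "mean duration of all periods of failure to respond to severe hypoxaemia will be calculated". These infant means are compared by the method used for the primary outcome, a weighted linear mixed model.

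No condition on the current FiO2 appears in 6.10, in 2.2 or in the results tables, and the SAP names no maximum FiO2.

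Eligibility does not rule the situation out. Entry requires "Receiving CPAP support and supplemental oxygen (FiO 2 >0.21) for respiratory insufficiency", with no upper limit on FiO2 alone. The exclusion for likely CPAP failure is a judgement made at entry, about infants who "would otherwise qualify for surfactant therapy and/or mechanical ventilation at initial assessment were it available".

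**The concern.** FiO2 has a physical maximum. When an infant is already there and SpO2 is still below 80%, neither a nurse nor the algorithm can raise FiO2 further. Coded literally, 6.10 counts that time as a failure to respond, so the variable no longer measures what its label says.

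The SAP handles the opposite limit with care. In 3.4, severe hyperoxaemia without a fall in FiO2 is relevant only while the infant receives oxygen. Sections 6.5 and 6.6 carry the same restriction, and the primary outcome accepts 91-100% in room air. Each of these recognises that FiO2 cannot be lowered below room air. Section 6.10 has no matching condition at the upper limit.

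Of the three outcomes listed under the safety objective, this is the only one compared between modes that asks whether control responded. Time in which no response was possible would blur that comparison.

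**Working it through.** **The plan's own figures.** Section 6.10 states none. The one sizing figure in the SAP, 13 infants in 2.6, concerns the primary outcome. It reproduces with a two-sided paired t-test (difference 10, SD 10, alpha 0.05): power is 0.911 at n = 13 and 0.883 at n = 12. It does not depend on 6.10.

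**Does at-maximum time meet the definition?** Take an infant at maximum FiO2 with SpO2 below 80% for 30 s or more. The SpO2 condition is met. The no-increment condition is met because no increment is possible. No further condition applies, so the period counts.

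**Effect on mean duration (assumed inputs).** The SAP gives neither the maximum nor the time spent at it, so these figures are illustrations. Assume genuine no-response periods average 45 s per infant, and that one infant has a single unbroken spell at maximum FiO2. The means are unweighted.

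| Scenario | Calculation | Group mean |
|---|---|---|
| No at-maximum time | – | 45 s |
| 40 infants, 10-minute spell is that infant's only period | (39×45 + 600)/40 | 58.9 s |
| 40 infants, 1-hour spell is that infant's only period | (39×45 + 3600)/40 | 133.9 s |
| 40 infants, 10-minute spell plus four 45 s periods | infant mean (4×45 + 600)/5 = 156 s; (39×45 + 156)/40 | 47.8 s |
| 10 infants contribute, 10-minute spell is the only period | (9×45 + 600)/10 | 100.5 s |

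The 10-infant row matters because an infant with no qualifying period has no mean duration and drops out of this comparison.

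**Effect on the rate.** One unbroken spell is one episode: 1/24 = about 0.04 per hour for that infant, and 0.04/40 = about 0.001 per hour averaged over 40. The rate moves only if there are repeated dips below 80% at maximum FiO2. Assume genuine rates of 0.4/h manual and 0.1/h automated, a true manual/automated ratio of 4.0, and add at-maximum episodes:

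- Equal in both modes at 0.05, 0.1 or 0.2/h: 0.45/0.15 = 3.0; 0.5/0.2 = 2.5; 0.6/0.3 = 2.0.
- More in automated (manual 0.05/h; automated 0.1, 0.2 or 0.4/h): 0.45/0.2 = 2.25; 0.45/0.3 = 1.5; 0.45/0.5 = 0.9.
- More in manual (manual 0.4/h; automated 0.05/h): 0.8/0.15 = 5.3.

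Equal contamination pulls the ratio towards 1. Unequal contamination can move it either way.

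**The case against.** The strongest reply is that the case may be rare and that the safety assessment does not rest on 6.10. Infants judged likely to fail CPAP within 48 hours or clinically unstable are excluded. Severe hypoxaemia is reported whatever the FiO2 in 6.2 to 6.4 and 6.11, malfunctions are listed with their timing and nature (6.12), and Listing 2 shows the treatment at the time of each safety event. Staying on CPAP at maximum FiO2 after a deterioration is an inference from the exclusion wording; the SAP does not state it. The protocol, which the SAP cites for full design details, may hold a rule on this. All of that stands and limits the priority. It does not change what 6.10 would count if coded as written.

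Three stronger readings are tempting, and the document does not support them:

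- *Such periods will be logged as device deficiencies.* The effect column in 3.4 does list severe hypoxaemia beyond 30 s "without an increase in" FiO2. The same row also requires an inadequacy of the device and gives an error of algorithm, servomotor or alarm as the mechanism. A device correctly holding maximum FiO2 shows neither.
- *One deteriorating infant can dominate the episode rate.* The outcome counts periods lasting at least 30 s, not each block of 30 s, so one long spell adds a single event.
- *The prompter mode will look worse.* It may reach maximum sooner, but a slow mode's delays below 80% are themselves scored as failures and may create many periods. The direction is open.

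**Conclusion.** The point holds for the definition in 6.10 and the matching row in 2.2: time at maximum FiO2 is scored as control failure. This is a rule that misclassifies, not a detail left to another document. It mainly distorts mean duration. The episode rate is affected only by repeated dips at maximum FiO2.

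The size is unknown. In the 40-infant illustration the group mean of 45 s becomes anything from 47.8 s to 133.9 s. The upper end needs an unbroken hour below 80% in an infant with no other qualifying period. The 45 s, the spell lengths and the episode rates are all assumptions. If maximum FiO2 is never reached during severe hypoxaemia, the effect is zero.

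The priority is minor. One secondary safety outcome is affected.

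**What to change.** In 6.10, and wherever its results are tabulated:

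- Let the 30 s clock run only while SpO2 is below 80% and recorded FiO2 is below the maximum deliverable value, and state that value in the SAP. If FiO2 is lowered from maximum while SpO2 is below 80%, the clock starts at that moment, so a genuine control failure still counts. A filter that required FiO2 to be below maximum throughout the whole hypoxaemic period could lose such a failure.
- Report the number and duration of periods with SpO2 below 80% at maximum FiO2 as a separate descriptive line by mode, so that no severe hypoxaemia is hidden.
- Carry the same wording into the matching row of the objectives table in 2.2. The definition in 3.4 needs no change on this account.

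The cost is a short wording change, one filter on FiO2 data that the outcome already uses, slightly fewer countable periods and one extra table row. The rule should be fixed before any comparison between modes is seen.
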